8.4.3.1.5 Clinical disease progression

Clinical disease progression symptoms will be summarised.

#### 8.4.3.1.6 Time to disease progression

Median time to PSA progression (deaths censored) by PCWG3 criteria (Scher HI et al., 2016) and median time to radiographic progression (deaths censored) by RECIST 1.1 (Eisenhauer EA et al., 2009) and PCWG3 criteria (Scher HI et al., 2016) will be summarised with descriptive statistics and Kaplan-Meier method.

## 8.4.3.1.7 Duration of objective response

Duration of objective response is defined as time from complete response or partial response to radiographic progression of disease, unequivocal clinical progression or death, duration of objective response will be summarised using descriptive statistics.

## 8.4.3.1.8 Radiographic progression-free survival (rPFS)

Radiographic progression-free survival (rPFS) is defined as time from enrollment (i.e. decision for entry) to radiographic progression or death from any cause. If patient experiences no event, the patient will be censored. rPFS will be summarised with descriptive statistics and Kaplan-Meier method.

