# 6.1.6.4 Part 2/Phase 2 only: Survival follow-up (added in Amendment 12)

Each patient will be followed for survival starting from the last study visit or possible adrenal recovery follow-up call. This will be performed by telephone, e-mail, chart review, or review of public records, in compliance with local practices and regulations. Patients who discontinue study treatment will move into survival follow-up and will be contacted at least every 12 weeks to assess for survival status until death, loss to follow up, or withdrawal of consent, whichever occurs first. Where possible, cause of death and further treatments for prostate cancer since the last follow-up will be recorded.

The sponsor may request updated survival status during the study before final analysis. Survival follow may continue for up to 2 years after the EOS visit for the last patient.

Investigators should attempt to also follow up and acquire survival status for subjects whose EOS visit precedes Amendment 12 coming into effect. For such patients the investigator should use available means to establish patient status before approaching the patient for further survival follow-up (for which patients will be asked to provide additional informed consent).

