#### 6.2.1.2 Soft tissue response

Chest, abdomen and pelvic CT or MRI will be performed at screening, and then every 8 weeks until week 24 and every 12 weeks thereafter (see section 6.1 for timings). Same imaging modality (CT or MRI) per patient should be used throughout the study. Objective response rate (ORR) of soft tissue (visceral or nodal disease) will be assessed by RECIST 1.1.

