# 6.2.1.4 ECOG performance status and clinical progression

ECOG performance status will be assessed at every visit during ODM-208 treatment (see section 6.1).

Clinical progression will be assessed. See 3.3.7 for details in definition of clinical progression.

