# 8.2 Estimation of sample size

No formal sample size calculation was performed. Separate dose escalation (3+3) will be performed in Part 1A Group 1 and Part 1A Group 2.

The purpose of the extension to the phase 2 expansion, introduced in Amendment 12, will be to achieve 2 cohorts of approximately 60 subjects per cohort under phase 2 conditions with and without AR LBD mutations to enable more accurate estimate of PSA response and rPFS, to support phase 3 study design as well as giving balance between the AR LBD mutation negative and positive patient population.

Simon's two-stage design (Simon R, 1989) was used to estimate the number of AR LBD mutation negative mCRPC patients in Part 2 extension (added in Amendment 12). The null hypothesis that the true PSA response rate is 5% will be tested against a one-sided alternative. Criteria for continuation of patient enrolment may be met at any time during the conduct of the study. However, if not met, then in the first stage, 23 subjects will be enrolled. If there are one or fewer PSA responses in these 23 subjects, the study will be stopped, otherwise, enrolment will continue as planned. The null hypothesis will be rejected if six or more PSA responses are observed in 56 patients. This design yields a significance level of 0.05 and power of 80% when the true response rate is 15%.

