# 8.4 Statistical analyses

Statistical analyses are described in more detail in the statistical analysis plan.

All evaluations will be performed for observed cases only and data will be presented separately by study part (Part 1, Part 2-), pooled over study parts and by dose level and by AR LBD mutation status, asif appropriate.

Confidence intervals (CIs): A two-sided type I error rate of 0.05 together with estimated 95% CIs will be used in this study.

Missing values and outliers: Statistical analysis will be performed for observed cases only. Possible sensitivity analyses may be carried out to evaluate the robustness of the statistical results, particularly the impact of potential outliers.

Missing event occurrence dates will be imputed as the earliest possible date. Missing event dates e.g., due to withdrawal of consent, lost to follow up or not known to have died at the analysis cut-off date, will be right censored (e.g. using last assessment in the study). Detailed methods are described in the statistical analysis plan.

Data transformations: PK parameters (at least AUC and  $C_{max}$ ) will be analysed after logarithmic transformation and the geometric mean will be calculated. Appropriate transformations may be used to analyse other parameters if found to improve conditions underlying the use of statistical methods.

Baseline is defined as last available measurement before study treatment starts. In case several measurements are taken at baseline, a mean value of measurements is used as a baseline.

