#### 8.4.3.1.4 ECOG performance status

The ECOG performance status and the changes from baseline will be summarised with descriptive statistics. Time to ECOG deterioration will be measured from enrolment to deterioration of ECOG >1 point. Patients who do not experience event or die will be censored.

Time to ECOG deterioration will be summarised with descriptive statistics and Kaplan-Meier method.

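### In Part 2, scanning ends with ODM-208 but rPFS counts deaths at any later time, so progression unseen after stopping is dated to death and rPFS is lengthened

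*Protocol*

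**What the plan says.** **Endpoint.** Section 8.4.3.1.8: "Radiographic progression-free survival (rPFS) is defined as time from enrollment (i.e. decision for entry) to radiographic progression or death from any cause". It continues: "If patient experiences no event, the patient will be censored". No censoring date is given there. Section 8.4 says that missing event dates "will be right censored (e.g. using last assessment in the study"), and leaves the detail to the SAP.

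**Scans.** Section 6.2.1.2 says that CT or MRI "will be performed at screening, and then every 8 weeks until week 24 and every 12 weeks thereafter". Section 6.2.1.3 sets the same times for bone scans. Both refer to section 6.1 for timing. In Table 3 the scan rows are marked at screening and at the on-treatment visits only. The +14-day, EOS, follow-up and survival columns have no scan. Section 3 says that the treatment visits run until ODM-208 is stopped, and the EOS list in 6.1.6.2 includes PSA but no imaging.

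**After stopping.** Section 6.1.6.4 provides survival contacts at least every 12 weeks in Part 2, for up to 2 years after the last patient's EOS visit. Their content is survival status and this: "Where possible, cause of death and further treatments for prostate cancer since the last follow-up will be recorded".

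**ECOG.** Section 6.2.1.4: "ECOG performance status will be assessed at every visit during ODM-208 treatment". Section 8.4.3.1.4, on time to ECOG deterioration: "Patients who do not experience event or die will be censored".

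**Use of rPFS.** Section 8.2 gives the purpose of the Amendment 12 cohorts as "to enable more accurate estimate of PSA response and rPFS, to support phase 3 study design".

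**The concern.** The endpoint looks for two kinds of event, but after ODM-208 stops the Part 2 schedule can find only one of them. Progression is no longer sought, while death is followed for years.

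Stopping without radiographic progression is foreseen. Section 3.3.7 bases progression on PSA, imaging and clinical status, and describes clinical progression as deterioration that objective methods cannot document. Section 4.5 adds toxicity, an interruption of more than 14 days and the patient's own decision. No scan is required at or after stopping, and beyond week 24 the last one may be up to 12 weeks old.

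At stake is the rPFS estimate that is to inform phase 3 planning. An SAP can choose censoring dates, but it cannot supply progression data that were never collected.

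**Working it through.** **1. The plan's own figures.** The protocol gives no event count, precision or power for rPFS, so there is no rPFS figure to reproduce. Its only formal design is the Simon two-stage rule on PSA response in the mutation-negative cohort (section 8.2). The probability of rejection is the sum over x = 2 to 23 of P(X1 = x) × P(X2 ≥ max(0, 6 − x)), with X1 ~ Bin(23, p) and X2 ~ Bin(33, p). This gives 0.04996 at p = 5% and 0.8003 at p = 15%, matching the stated 0.05 and 80%. It has no bearing on rPFS.

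**2. Direction for patients who die.** Take a patient who stops without radiographic progression. Let P be the date on which the continued scan schedule would first have shown progression, and D the date of death.

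- With scans continued: rPFS = min(P, D).
- As written: rPFS = D.
- Difference: D − min(P, D) = max(0, D − P), which is never negative.

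Hypothetical case: scans at weeks 8 and 16, stop at week 20, progression that a week-24 scan would have shown, death at week 60. The written rule gives 60 weeks instead of 24, so 60 − 24 = 36 weeks too long.

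**3. Direction for patients censored alive.** If they are censored at their last scan, Kaplan-Meier treats them as sharing the later risk of those still scanned. If stopping signals faster progression, rPFS is too high. If it does not, rPFS need not be too high and can be too low.

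**4. Illustration of size.** None of these inputs is in the protocol. Assumed: median time to radiographic progression 14 or 26 weeks; 20%, 40% or 60% stopping first; hazard ratio (HR) for progression after stopping 0.5, 1, 2 or 3; median 40 weeks from progression to death; exponential times; scans at weeks 8, 16, 24, then every 12 weeks; 200,000 simulated patients per scenario. Three treatments of the stoppers are compared with continued scanning:

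- (a) all censored at the last on-treatment scan;
- (b) deaths to week 156 are events, survivors censored at week 156;
- (c) as (b), but survivors censored at the last scan.

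Kaplan-Meier rPFS at 24 weeks, median 14 weeks, 40% stopping:

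| HR after stopping | Scans continued | (a) | (b) | (c) |
|---|---|---|---|---|
| 0.5 | 0.38 | 0.27 | 0.47 | 0.44 |
| 1 | 0.30 | 0.26 | 0.45 | 0.44 |
| 2 | 0.23 | 0.26 | 0.44 | 0.42 |
| 3 | 0.19 | 0.26 | 0.43 | 0.42 |

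Difference from continued scanning at 24 weeks, over all scenarios:

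- (b): 0.02 to 0.40 higher;
- (c): from no difference to 0.38 higher;
- (a): 0.01 to 0.11 higher at HR 2 or 3, but 0.01 to 0.22 lower at HR 1 or less.

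Medians are a poor yardstick, because detected progressions fall on the scan grid. At HR 2 in the table, the median is 16 weeks with scans continued, 16 under (a) and 24 under (b) and (c), a jump of one scan interval.

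**5. ECOG.** The ECOG row of Table 3 ends at the on-treatment visits. The +14-day visit (6.1.6.1.2) and the EOS visit (6.1.6.2) include a physical examination but no ECOG rating. A patient who deteriorates between his last treatment visit and stopping, or soon after, has no rating to show it.

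**The case against.** **The scan sections state no end.** Sections 6.2.1.2 and 6.2.1.3 could be read as scanning regardless of treatment. But they defer to section 6.1, and Table 3 ties the scans to visits that end with treatment.

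**The SAP may deal with it.** This stands for the censoring date and for sensitivity analyses, which the protocol leaves to the SAP; the lack of a date in 8.4.3.1.8 is no fault. It does not stand for the missing data, nor for the definition, which already counts any death.

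**Both routes flatter ODM-208.** A reader might infer this, but it is not supported. Only the death route has a fixed sign. Early censoring can bias rPFS downward, as column (a) shows, and stops for toxicity or interruption need not predict progression. The death route is also confined to Part 2, because survival follow-up is.

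**The inflation can be quantified.** A reader might take the simulated shift as an estimate. It is not: the protocol gives neither the share of such stops nor the risk after stopping. Treatment may also continue past progression if judged beneficial, so PSA progression need not end scanning.

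**Death should count as ECOG deterioration.** A reader might infer this too. Section 8.4.3.1.4 openly censors deaths, and counting them would define a different endpoint. The ECOG point is only the missing ratings.

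**Little depends on rPFS.** There is no hypothesis on rPFS, it is summarised descriptively, and the only decision rule uses PSA response. This limits the consequence. But section 8.2 names rPFS as a reason for the expansion.

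**Conclusion.** The point holds for Part 2. Radiographic progression is not collected after ODM-208 stops, while deaths at any later time count as rPFS events. For a patient who progresses unseen and then dies, the error is zero or positive, and this needs no assumption. For patients censored alive, the bias is upward only if stopping is informative.

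The overall size is unknown. It depends on how many patients stop without radiographic progression and on their risk afterwards, and the documents give neither. The simulated range shows only that the effect could be anything from negligible to large. ECOG deterioration at or just after stopping can be missed, by an amount that cannot be stated.

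This does not touch the PSA decision rule. It should be corrected before the rPFS estimate is used for phase 3 design.

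**What to change.** 1. In section 6.1.6.4, at the existing 12-weekly contacts, record the date and result of any routine CT/MRI or bone scan up to first radiographic progression or new anticancer therapy. Use these for rPFS in 8.4.3.1.8.
2. Keep the defined rPFS and add two sensitivity analyses meant to bracket it: (i) deaths after two or more missed scheduled scan intervals censored at the last scan; (ii) discontinuation for PSA or clinical progression counted as an event. Two intervals are 2 × 8 = 16 weeks early on and 2 × 12 = 24 weeks after week 24. Analysis (i) alone is no cure, since censoring at the last scan is itself biased when stopping is informative.
3. Add an ECOG rating to the +14-day and EOS columns of Table 3 and to sections 6.1.6.1.2 and 6.1.6.2.

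Cost: a few CRF fields at contacts already planned, one rating at each of two existing visits, and some wording. Routine scans are less standardised in timing and modality than protocol scans, so progressions found this way should be flagged in the report.

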#### 8.4.3.1.9 Time on treatment

The time from the start of ODM-208 treatment until discontinuation of ODM-208 treatment will be summarised with descriptive statistics and Kaplan-Meier method, if appropriate.

#### 8.4.3.1.10 Part 2/Phase 2 only: CTC response

The proportion of patients with CTC response (CTC0) will be presented. CTC responses will be tabulated using descriptive statistics. In addition, a proportion of patients achieving a decline  $\geq$  30% from baseline in CTC count will be tabulated.

#### 8.4.3.1.11 Overall survival (OS)

Overall survival (OS) is defined as time from enrolment (i.e. decision for entry) to date of death from any cause. The date and cause of death will be recorded. Status of OS will be assessed until end of study. The OS distribution will be estimated using Kaplan-Meier method and Kaplan-Meier curves including median survival times and their 95% confidence intervals will be reported.

#### 8.4.4 Pharmacokinetic analysis

The PK variables ( $C_{max}$ ,  $t_{max}$ , AUCt, AUC $_{\infty}$ ,  $V_z/F$ , Cl/F and  $t_2$ ) will be summarised separately after single and repeated dosing using descriptive statistics, and plotted with appropriate figures.

In Part 1, the dose proportionality of ODM-208 on the PK variables AUCt and  $C_{max}$  will be analysed using a general linear regression model ('power model') for the log-transformed AUCt and  $C_{max}$  values. The comparison of PK results of ODM-208 between single dose and repeated dose administration will be made by a linear mixed model, including sampling day as repeated factor, and dose level as a between factor.

## 8.4.5 Pharmacodynamic analyses

## 8.4.5.1 Steroid variables

The actual values and the changes from baseline for testosterone and other steroid variables will be summarised using descriptive statistics.

## 8.4.6 Analysis of explorative plasma assessments

The role of specific activating AR LBD mutation in antitumor activity will be examined and tabulated using descriptive statistics.

AR amplification and AR-V7 (Part 2 only) data will be tabulated using descriptive statistics, and their relationship to antitumor activity of ODM-208 will be examined. Other identified genetic alterations will be tabulated using descriptive statistics.

Explorative analyses will aim to identify circulating factors such as nucleic acids, proteins and biochemical metabolites. Plasma biomarker results may be reported in separate reports, as appropriate.

## 8.4.7 Population pharmacokinetic/pharmacodynamic analysis

A population PK and PK/PD model for ODM-208 is planned to be developed. Population PK and PK/PD modelling may be applied to evaluate the role of covariates and PK/PD relations in terms of safety and efficacy related endpoints. Details of the modelling and possible simulation process will be described in a separate population PK/PD modelling plan.

#### 8.4.8 Analysis of germline DNA and pharmacogenetics

Genetic polymorphisms may be analysed in relation to significant variation or specific scientific question in PK, PD or safety variables of ODM-208. If such analysis will be performed, the results will be reported in separate reports.

#### 8.4.9 Safety analysis

#### 8.4.9.1 Analysis of adverse events

AEs reported during the study will be classified by system organ classes and preferred terms using the Medical Dictionary for Regulatory Activities (MedDRA) coding system. The AEs as event counts and subject counts will be displayed with frequency tables. The number and proportion (%) of patients having each AE will be given.

The AEs will be graded by toxicity grade classified by NCI CTCAE version 4.03. Severity is included in this grading and there is no separate severity assessment. Incidences of AEs will also

be summarised by maximum severity. SAEs and other significant AEs will be evaluated caseby-case. Occurrence of DLTs (Part 1 only) will be summarised with descriptive statistics. AEs occurring before, after the initiation of study treatment and post treatment will be listed.

## 8.4.9.2 Clinical safety analysis

#### 8.4.9.3 Vital signs

Vital signs, and orthostatic test (Part 1 only) will be summarised using descriptive statistics. The absolute values and the changes in vital signs from baseline will be shown. Abnormal orthostatic test (drop in systolic BP of  $\ge$  20 mmHg, or in diastolic BP of  $\ge$  10 mmHg) will be tabulated by time point (Part 1 only).

Orthostatic values will be tabulated according to normal, clinically not relevant abnormality and clinically relevant abnormality (Part 1 only).

#### 8.4.9.4 12-lead ECG

The actual values and corresponding changes from baseline for ECG variables (RR, PR, QT, QRS, QTc-Bazett and QTc-Fridericia) will be summarised using descriptive statistics.

Interpretation of 12-lead ECG will be tabulated (normal, clinically not relevant abnormality and clinically relevant abnormality). The number of patients with QT or QTc-Fridericia prolongation will be tabulated. The prolongation criteria for QT and QTc-Fridericia are as follows:

- > 450 ms
- > 470 ms
- > 500 ms
- increase of 30 to 60 ms from baseline
- increase of > 60 ms from baseline

Concentration-QTc-Fridericia relationship will be examined to evaluate proarrhythmic risk. A line-scatter plot with linear regression fit for QTc-Fridericia change from baseline and ODM-208 with 1-sided 95% CI will be produced.

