- 13. Clinically significant abnormal serum potassium or sodium level.
- 14. Active or unstable cardio/cerebro-vascular disease, including thromboembolic events. Examples include recent (within 6 months) myocardial infarction, coronary artery bypass graft or symptomatic cerebrovascular accident or congestive heart failure (New York Heart Association class II-IV (for **Part 1/Phase 1**), III-IV (for **Part 2/Phase 2**).

- 15. History or family history of long QTc syndrome. Repeatable prolongation (2 out of 3 recordings) of QTcF interval > 450 ms (for **Part 1/Phase 1**), > 470 ms (for **Part 2/Phase 2**), or any clinically significant abnormality in the centrally-read ECG.
- 16. Major surgery within 4 weeks before the start of the study treatment.
- 17. Severe or uncontrolled concurrent medical condition or psychiatric illness.
- 18. Serious persistent infection within 2 weeks prior to the start of the study treatment.
- Part 1/Phase 1 (Finland, France and UK) and Part 2/Phase 2 (France and UK): Known history of human immunodeficiency virus (HIV), or acute or chronic hepatitis B or hepatitis C disease.
   Part 2/Phase 2 (US and Finland): Patients with HIV on established antiretroviral therapy (ART) less than four weeks and/or an HIV viral load more than 400 copies/mL prior to enrolment (added in Amendment 8).
- 20. Known hypersensitivity to study treatment or any of its ingredients.
- 21. Participation in another interventional clinical trial with an investigational agent or any concurrent treatment with any investigational drug 4 weeks (immune checkpoint inhibitors 12 weeks) prior to the start of the study treatment.
- 22. Systemic use of the following medications within 2 weeks prior to the start of study treatment (added in Amendment 8):
  - Strong CYP3A4 inducers: E.g. avasimibe, carbamazepine, lumacaftor, phenobarbital, rifampicin, rifapentine, St John's Wort
  - P-gp inhibitors: erythromycin, clarithromycin, rifampicin, ketoconazole, itraconazole, posaconazole, artesunate-pyronaridine, ritonavir, indinavir, nelfinavir, atazanavir, glecaprevir-pibrentasvir, simeprevir, ledipasvir-sofosbuvir, verapamil, diltiazem, dronedarone, propafenone, quinidine, cyclosporine, valspodar, milk thistle (Silybum marianum)

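### The > 450 ms QTcF prolongation row has no baseline condition, so in Part 2, which admits QTcF up to 470 ms, it counts eligible patients who have not changed; the same limits on uncorrected QT misclassify with heart rate

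*Protocol*

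**What the plan says.** Section 8.4.9.4 plans a categorical ECG table: "The number of patients with QT or QTc-Fridericia prolongation will be tabulated". A single list serves both variables: "The prolongation criteria for QT and QTc-Fridericia are as follows", followed by > 450, > 470 and > 500 ms, "increase of 30 to 60 ms from baseline" and "increase of > 60 ms from baseline". Only the last two refer to baseline. The section also summarises actual values and changes for the ECG intervals, including RR, QT and QTcF, and plots QTcF change against ODM-208 concentration.

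Exclusion criterion 15 in section 4.3 sets a different entry limit in each part. For Part 1 it is "Repeatable prolongation (2 out of 3 recordings) of QTcF interval > 450 ms"; for Part 2 it is "> 470 ms (for Part 2/Phase 2".

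Section 8.4 says data are shown by study part and also "pooled over study parts", as appropriate. It defines baseline as the last measurement before treatment, averaged if there are several. Section 6.5.4.3 gives triplicate ECGs at screening and before dosing on Day 1, and single recordings otherwise.

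**The concern.** The table is labelled prolongation, but an absolute limit with no baseline condition counts values, not changes. In Part 1 the entry limit equals the first row, so a patient in that row has, recording noise aside, moved there on treatment. In Part 2 the entry limit is 20 ms higher. A patient with QTcF of 451-470 ms is eligible and meets the first criterion before his first dose. The row therefore has a different meaning in each part, and a pooled row mixes the two. The study has no control group against which such a background count could be set.

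Secondly, the same millisecond limits are applied to QT not corrected for heart rate, so a slow rate can create a case and a fast rate can conceal one.

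What is at stake is how a descriptive safety table is read. Safety and tolerability are a primary objective of Part 2 (section 2.1), and section 8.4.9.4 describes no other table of counts above QT limits.

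**Working it through.** The protocol states no figure that could be reproduced here. The check sets the entry rule against the counting rule and then sizes the gap.

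**1. One unchanged patient.** Take a Part 2 patient with QTcF 460 ms before and after dosing.
- Entry: 460 is not above 470, so he is eligible.
- Limits: 460 > 450 is met; > 470 and > 500 are not.
- Change: 460 − 460 = 0, so neither increase criterion is met.

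He adds one to the > 450 ms row and nothing elsewhere. If only newly exceeded limits counted, he would add nothing.

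**2. How many such patients.** Section 8.2 plans two Part 2 cohorts of about 60, so about 120. The protocol does not give the baseline QTcF distribution. Assume it is normal with mean m and SD 20 ms, truncated at 470 ms. The share at 450-470 ms is

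[Φ((470 − m)/20) − Φ((450 − m)/20)] / Φ((470 − m)/20)

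| Assumed mean m | Share at 450-470 ms | Of 120 |
|---|---|---|
| 410 ms | 0.021 | 2.6 |
| 420 ms | 0.061 | 7.3 |
| 430 ms | 0.139 | 16.7 |

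This gives about 3, 7 or 17 patients.

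**3. The other absolute rows.** Two routes lead an unchanged patient into the > 470 ms row.
- The 2-of-3 rule admits readings of 465, 468 and 490 ms, whose mean is 1423/3 = 474.3 ms.
- Post-dose recordings are single. Part 2 has 14 up to week 24: three on Day 1 (2, 6 and 12 h) and one at each of Visits 2 to 12. With an assumed within-patient SD s and independent errors, a patient truly at 460 ms exceeds 470 ms at least once with probability 1 − Φ(10/s)^14. That is 0.28 for s = 5 ms and 0.91 for s = 10 ms.

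The same noise reaches the > 450 ms row from below. A patient truly at 445 ms exceeds 450 ms at least once in 14 recordings with probability 0.91 at s = 5 ms, so the Part 1 row is not a clean count of new values either.

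**4. Uncorrected QT.** Fridericia: QTcF = QT / (60/HR)^(1/3).
- Slow rate: QT 450 ms at 50/min gives 450 / 1.2^(1/3) = 423.5 ms. A patient with QTcF 430 ms meets QT > 450 ms at any rate below 60 / (450/430)³ = 52.4/min.
- Fast rate: QTcF 480 ms at 90/min is QT 480 × (60/90)^(1/3) = 419 ms, and QTcF 510 ms is QT 445.5 ms. Neither meets any absolute QT limit.
- Change in rate: at a constant QTcF of 430 ms, QT is 390.7 ms at 80/min and 430.0 ms at 60/min. That increase of 39.3 ms falls in the 30-60 ms row with no change in QTcF.

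The protocol reports no heart rates. Section 5.7.4 permits beta-blockers with caution, so slow rates are plausible.

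**The case against.** The strongest reply is that the same section already separates change from level. The patient who stays at 460 ms meets neither increase criterion, and the change summaries and the concentration-QTcF plot are unaffected by the entry limit. The > 470 ms row sits exactly at the Part 2 entry limit, so Part 2 has a row that starts where eligibility ends. This stands, and it confines the QTcF problem mainly to the > 450 ms row in Part 2 and pooled tables.

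A reader might infer that genuine new cases are hidden, or that Part 2 will be judged worse than Part 1. The documents do not support either. A true shift in QTcF shows in the change rows. Results are presented by part as well as pooled, and no comparison of ECG results between parts is planned. Nor does the protocol say that the five criteria are merged into one count; a list of five reads more naturally as five rows. If they were merged, the distortion would be larger.

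It can also be said that restricting rows to new post-baseline values is detail for the statistical analysis plan, to which section 8.4 refers and which is not at hand. It may do so. The point remains because the protocol itself fixes the limits, applies them to both QT and QTcF, and attaches baseline to two of the five criteria only. Followed literally, that rule misclassifies.

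Finally, the patient numbers rest on an assumed distribution. Criterion 15 also excludes clinically significant abnormalities on central ECG reading, which could lower them. This stands as well. For uncorrected QT, it is fair that QTcF is tabulated beside it and RR is summarised, so a careful reader could spot a rate effect; the QT rows would still be wrong as labelled.

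**Conclusion.** The point holds for the > 450 ms QTcF row in Part 2 and in tables pooled over parts: it counts eligible patients whose QTcF has not changed, and it differs in meaning from the Part 1 row. The existence of the problem follows from the text alone. Its size does not: about 3, 7 or 17 of about 120 rests on an assumed normal baseline with mean 410, 420 or 430 ms and SD 20 ms. The other QTcF rows are largely unaffected apart from measurement noise, which the single post-dose recordings can make appreciable near a limit.

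The misclassification of uncorrected QT in both directions is plain arithmetic; how often it occurs depends on heart rates that the protocol does not report.

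This is a minor to moderate flaw in a descriptive safety table. It touches no efficacy result, error rate or stopping rule. It does not show that the Part 2 entry limit is wrong, and no change to eligibility follows from it.

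**What to change.** Amend section 8.4.9.4 as follows.
- Apply the three absolute limits to QTcF only. Count a patient in a row when a post-dose QTcF exceeds a limit that his baseline QTcF did not exceed.
- Add a shift table of baseline category by worst post-dose category for QTcF, by study part.
- Keep the two change-from-baseline rows for QTcF, and keep uncorrected QT in the descriptive summary only.

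All the data are already collected. The cost is a sentence or two and one extra table. The drawback is that patients with high baselines leave the absolute-limit rows. One moving from 455 to 469 ms gains 14 ms, so he would meet neither the 30 ms increase nor the 470 ms limit. The shift table keeps him visible as a high-baseline patient, and his change remains in the summary of changes.

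The fix does not remove noise from single recordings, so a value just above a limit still needs to be read against its baseline.
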